15.1.3 Documentation of Adverse Events

From the time informed consent is signed through the last study visit all adverse events will be collected. The following data should be documented for each adverse event:

- Description of the event
- Classification of "serious" or "not serious"
- Date of first occurrence and date of resolution (if applicable)
- Causal relationship to inhaled nitric oxide exposure
- Action taken

NO-NTM

- Outcome
- Concomitant medication or other treatment given

15.1.4 Adverse Event Causality

Every effort should be made by the investigator to assess the relationship of the adverse event, if any, to inhaled nitric oxide exposure. Causality should be classified using the categories presented in Table 15-1.

Table 15-1 Classification for Adverse Event Causality	
Classification	Definition
Related	There is a suspected association between the event and the administration of inhaled nitric oxide , a plausible mechanism for the event to be related to inhaled nitric oxide and causes other than the inhaled nitric oxide have been ruled out, and/or the event re-appeared on re-exposure to inhaled nitric oxide .
Not related	The event is believed related to an etiology other than the inhaled nitric oxide . (The alternative etiology should be documented in the study subject's medical record)

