10 SELECTION OF STUDY POPULATION

10.1 Inclusion Criteria

Patients with NTM lung disease who persistently demonstrate infection with positive sputum cultures will be eligible for the study. This will include patients with and without CF as this is typical of the NTM population and this therapy should be non-discriminatory. Inclusion criteria are as follows:

- Subjects are ≥ 18 years of age and able to provide informed consent.
- Subjects have NTM lung disease as defined by each of the following:
 - Sputum cultures positive for NTM (MAC or *M. abscessus*)
 - Radiologic studies that demonstrate features consistent with disease such as nodular bronchiectasis and/or cavities
 - Symptoms consistent with disease including respiratory (e.g. cough, sputum production, hemoptysis, chest pain) and constitutional (e.g. fevers, night sweats, fatigue, myalgias, arthralgias, weight loss)
- Subjects are able to produce sputum for culture (either spontaneous or induced).
- Subjects have a history of persistently positive sputum cultures for NTM defined as
 - ≥ 2 positive cultures over the preceding 6 months AND
 - Has not met the definition for culture clearance in the last 6 months (three negatives in a row)
- Clinically stable with no significant changes in health status within 14 days prior to Screening or Day 1
- Subjects are willing and able to perform requirements of the study.

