13.2 Withdrawal from study

If a subject experiences any of the following events during the study period, they should be immediately be withdrawn from the study.

Study drug related adverse events:

- Two consecutive inhalation treatment periods with a persistent absolute increase in methemoglobin of more than 5% above the Day 1 baseline value
- Study drug related significant hemoptysis: production of greater than 50 mL blood in a 24 hour period. Note: Standard treatment for significant hemoptysis should include immediate chest x-ray, hematocrit measurement and if frothy sputum present, an evaluation for hemosiderin labeled macrophages.
- Any study drug related adverse event that repeats upon treatment continuation.

NO-NTM

Other withdrawal criteria:

- At the discretion of the subject
- At the discretion of the Investigator, if deemed appropriate, for any reason
- Subjects will also be withdrawn from the study if they have had to discontinue treatment during the 50-minute inhalation period more than twice due to criteria listed in 13.1.

If a subject is withdrawn because of an adverse event, the subject will be followed and treated by the Investigator until the abnormal parameter or symptom has resolved or stabilized.

The adverse events must be followed to resolution and the follow-up evaluations should be performed when the subject has stabilized.

If for any reason a subject does not complete the study, the reason will be entered on the CRF. All subjects are free to withdraw from participation at any time, for any reason, specified or unspecified, and without prejudice. The Investigator must record the reason for the early termination.

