14.3.3.1 Adverse Events

All adverse events with start date on or after enrollment date through the last study visit will be summarized. Adverse events are defined in Section 15.1.1. Adverse event summary tables will include the following:

- all adverse events;
- related (identified as related to inhaled nitric oxide by the investigator) adverse events;
- adverse events leading to treatment discontinuation;
- serious adverse events (SAEs); and
- adverse events by relationship.

Summaries will be presented by MedDRA system organ class and preferred term using frequency counts and percentages. A subject with multiple occurrences of the same adverse event or a continuing adverse event will be counted only once, by relationship.

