15.1.2 Definition of a Serious Adverse Event

An SAE is any adverse event that meets any of the following criteria:

- Fatal (death, regardless of cause, that occurs during participation in the study, or occurs after participation in the study and is suspected of being possibly related to inhaled nitric oxide).
- Life-threatening, such that the subject was at immediate risk of death from the reaction as it occurred.
- Inpatient hospitalization or prolongation of hospitalization, with the exception of planned or elective hospitalization.
- Persistent or significant disability/incapacity (disability is defined as a substantial disruption of a person's ability to conduct normal life functions).
- Congenital anomaly or birth defect.
- Important medical event that, based upon appropriate medical judgment, may jeopardize the subject or may require medical or surgical intervention to prevent 1 of the outcomes listed above (e.g., an allergic bronchospasm requiring intensive treatment in an emergency room or at home).

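### Table 15-1 has no class for a suspected, plausible adverse event whose other causes are not excluded and which has not recurred, so the related-event summaries are likely to under-count or to be inconsistent

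*Combined protocol and SAP*

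**What the plan says.** Section 15.1.4 tells the investigator that "Causality should be classified using the categories presented in Table 15-1", and the table holds only Related and Not related. The entry for Related opens with "There is a suspected association between the event and the administration of inhaled nitric oxide", adds a plausible mechanism, and requires that "causes other than the inhaled nitric oxide have been ruled out". It closes with a further route: "and/or the event re-appeared on re-exposure to inhaled nitric oxide". Not related is also a positive finding. The investigator must believe in a different cause and should document it.

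The class is used, or echoed, in three other places:

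- Section 14.3.3.1 plans five adverse event summaries. Two use the class: "related (identified as related to inhaled nitric oxide by the investigator) adverse events", and events by relationship.
- Section 13.2 withdraws subjects for certain drug-related events. These include significant hemoptysis and "Any study drug related adverse event that repeats upon treatment continuation".
- Section 15.1.2 counts a death after participation as serious if it "is suspected of being possibly related to inhaled nitric oxide".

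On the population, section 10.1 makes symptoms part of the entry definition: "Symptoms consistent with disease including respiratory (e.g. cough, sputum production, hemoptysis, chest pain", followed by constitutional symptoms. The special-interest list (the second section numbered 15.1.6) includes cough, hemoptysis, bronchospasm, bronchitis and acute hypoxia.

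**The concern.** A two-class scheme works only if every event falls into one class. Here both classes ask for a positive judgment, and the ordinary uncertain event satisfies neither. That event is one that might be due to gNO or to the lung disease, with no means of telling which.

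The gap matters more here than in most trials. Safety and tolerability are a secondary endpoint. There is no control arm to show the background rate of respiratory events, so the investigator's causality call carries much of the weight. Several special-interest events can also be symptoms of the disease that brought subjects into the trial. If uncertain events drift into Not related, the related-event table will look cleaner than the data warrant. If the two sites settle the uncertainty differently, the table will mix two definitions.

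**Working it through.** The documents give no figure for this point, so the check is mainly one of logic, followed by a calculation of scale.

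**1. Does any event fall outside both classes?** Let S = suspected association, M = plausible mechanism, X = other causes ruled out, R = reappeared on re-exposure, B = another cause believed responsible. Not related is B. The and/or in the Related entry can be read in two ways:

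- Reading 1: (S and M and X) or R
- Reading 2: S and M and (X or R)

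| S | M | X | R | B | Related, reading 1 | Related, reading 2 | Not related |
|---|---|---|---|---|---|---|---|
| yes | yes | yes | no | no | yes | yes | no |
| yes | yes | no | yes | no | yes | yes | no |
| no | no | no | no | yes | no | no | yes |
| yes | yes | no | no | no | **no** | **no** | **no** |

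The last row has no class under either reading.

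**2. How far does the re-exposure route close the gap?** Section 11.1 plans three sessions a day on 15 days: 3 × 15 = 45 sessions, of which 44 follow the first. An acute event that comes back at a later session is caught. The route cannot help with:

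- an event that starts after the last session on Day 19. Events are collected to the last visit (15.1.3), which is Week 15 (Table 3-1), so about 15 − 3 = 12 of the 15 weeks from Day 1 lie after treatment;
- an event after which the subject is withdrawn;
- an event that continues without resolving and so cannot reappear.

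**3. Which outputs depend on the class?**

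| Depends on the class | Does not depend on it |
|---|---|
| Related-event summary (14.3.3.1) | All-event summary (14.3.3.1) |
| By-relationship summary (14.3.3.1) | Subject listings (14.3.3) |
| Drug-related criteria in 13.2, if read through Table 15-1 | Special-interest recording (second 15.1.6) |
| | SAE reporting to the IRB (first 15.1.6) |

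**4. Scale.** Section 14.1 gives 6 to 10 subjects. One subject is 1/10 = 10 points at the maximum and 1/6 = 16.7 points at the minimum.

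The exact (Clopper-Pearson) 95% limits for x of n are the 0.025 quantile of Beta(x, n − x + 1) and the 0.975 quantile of Beta(x + 1, n − x). For x = 0 the upper limit is 1 − 0.025^(1/n). At n = 10 this is 1 − 0.025^0.1 = 0.308, which agrees with the 0% to 31% that 14.1 quotes for no responders.

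The number of subjects with a gap event is not in the documents. Assume three of 10, with no other related events:

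| Gap subjects classed Related | Rate shown | Exact 95% CI |
|---|---|---|
| 0 | 0/10 | 0-31% |
| 1 | 1/10 | 0.3-44% |
| 2 | 2/10 | 3-56% |
| 3 | 3/10 | 7-65% |

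With two gap subjects the range runs from 0/10 to 2/10 (3-56%). With four it runs from 0/10 to 4/10 (12-74%), and with six from 0/10 to 6/10 (26-88%). The plan calls for counts and percentages of adverse events, not intervals; the intervals here only convey scale.

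**The case against.** The other side has several good points.

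- **Related is not confined to events with every other cause excluded.** A reader who stops at the ruled-out clause might infer that it is. The same sentence adds the re-exposure route, and 45 planned sessions give acute events many chances to meet it. This stands, and it limits the concern to events that have not recurred.
- **Under-counting is not certain.** Not related is no default class, since it needs a believed alternative, so the text does not say where a gap event goes. This stands. Under-counting is the likelier direction because Related has the stricter test, but inconsistent classing is the other possible outcome.
- **The 13.2 withdrawal criteria are not generally disabled.** A reader might infer that they are. The criterion on events that repeat describes recurrence, which on a natural reading of the and/or meets the re-exposure route. The methemoglobin criterion is numeric, and withdrawal at the investigator's discretion needs no causality finding. Only the hemoptysis criterion is clearly exposed, because relatedness may have to be judged at the first episode, before any re-exposure.
- **The 15.1.2 wording is a capture rule for deaths after participation, not a rival classification.** This is fair. It still refers to a degree of suspicion for which Table 15-1 has no class.
- **Other causes can sometimes be excluded.** The symptoms in 10.1 are examples, subjects must be clinically stable, and an adverse event must be new or worsened (15.1.1). Monitoring during sessions also helps attribution. This rules out saying that exclusion is almost never possible. It does not supply a class for the cases where exclusion fails.
- **Safeguards exist.** The outputs that do not depend on causality, and an independent Medical Monitor who reviews all SAE reports (12.3.2), limit the harm. They do not correct the related-event rate.

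**Conclusion.** The concern holds in a limited form. Table 15-1 leaves without a class any suspected, plausible event whose other causes are neither excluded nor believed responsible and which has not reappeared. Both readings of the and/or give this result, so it rests on the text alone.

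That such events will occur, and will more often be left out of the related-event count than put in, is a judgment. It rests on the overlap between disease symptoms and special-interest events, and on the stricter test for Related. The effect is mainly on two of the five summaries in 14.3.3.1, at 10 points per subject with 10 subjects and more with fewer. The span from 0/10 to 3/10 is an illustration under an assumed count; its lower end is the worst case, in which no gap event is classed Related. The documents do not support saying that the overall safety record is biased or that the withdrawal rules fail as a set.

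**What to change.** In Table 15-1:

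- define Related as a reasonable possibility that gNO caused or contributed to the event, expressly including possibly related events and events that reappear on re-exposure. This also removes the ambiguity of the and/or;
- define Not related as no reasonable possibility, with the alternative cause documented.

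In 14.3.3.1, state that an event that cannot be assigned is counted as Related in the summary tables. In 15.1.2, align the phrase about possible relatedness with the new definition.

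Separately, the sponsor should reconcile what drug-related means in 13.2, notably in the hemoptysis criterion, with Table 15-1. No withdrawal rule is proposed here.

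The cost is a wording change in the protocol and in the CRF causality field. The downside is that more events will be shown as related, some of them caused by the disease. The all-event table and the listings will let a reader see those in context.

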15.1.5 Adverse Event Outcome

An adverse event should be followed until the investigator has determined and provided the final outcome. The outcome should be classified according to the categories shown in Table 15-2.

Table 15-2 Classifications for Outcome of an Adverse Event	
Classification	Definition
Recovered/Resolved	Resolution of an adverse event with no residual signs or symptoms
Recovered/Resolved with Sequelae	Resolution of an adverse event with residual signs or symptoms
Not Recovered/Not resolved (Continuing)	Either incomplete improvement or no improvement of an adverse event, such that it remains ongoing
Fatal	Outcome of an adverse event is death. "Fatal" should be used when death is at least possibly related to the adverse event
Unknown	Outcome of an adverse event is not known (e.g., a subject lost to follow-up).

15.1.6 Reporting Procedure for Adverse Events and Pregnancy

All serious events (as defined in Section 15.1.2) that occur after obtaining informed consent and assent (where applicable) through the last study visit, regardless of causality, will be reported to the MUSC IRB **within 24 hours** of their awareness.

15.1.6 Adverse events of special interest

NO-NTM

Short-term NO₂ exposures, ranging from 30 minutes to 24 hours, are associated with the following adverse respiratory effects: decreased pulmonary function, chronic bronchitis, dyspnea, chest pain, pulmonary edema, cyanosis, tachypnea, tachycardia, which can aggravate existing heart disease, leading to increased hospital admissions and premature death. We will monitor for and record the following adverse events of special interest: methemoglobinemia, acute hypoxia and hemoptysis, bronchospasm, nasal congestion, sinus congestion, sinusitis, cough, bronchitis, pneumonitis, and alveolitis, as well as nausea, vomiting and diarrhea.

15.2 Administrative Requirements

15.2.1 Ethical Considerations

The study will be conducted in accordance with the ethical principles founded in the Declaration of Helsinki, and according to local applicable laws and regulations. The institutional review board (IRB) will review all appropriate study documentation to safeguard the rights, safety, and well-being of the subjects..

15.2.2 Subject Information and Informed Consent

Subjects must also be informed that participation is voluntary and that they may withdraw from the study at any time, without prejudice to their current or future care. Documentation of the discussion and the date of informed consent must be recorded in the subject's medical record or a study/clinic chart. Once all of their questions have been answered and they have voluntarily agreed to participate in the study, each subject will be asked to sign and date the ICF. Informed consent must be obtained from each subject before the performance of any study-related activity.

15.2.3 Investigator Compliance

No modifications to the protocol should be made without the approval of the IRB, except where the modification is necessary to eliminate an apparent immediate hazard to human subjects. Any departures from protocol must be fully documented in the source documentation and in a protocol deviation log.

15.2.4 Access to Records

The records must also be available for direct inspection, verification, and copying, as required by applicable laws and regulations, by officials of the regulatory health authorities (FDA and others). The investigator must comply with applicable privacy and security laws for use and disclosure of information related to the research set forth in this protocol.

15.2.5 Subject Privacy

To maintain subject confidentiality, all case report forms (CRFs), study reports, and communications relating to the study will identify subjects by assigned subject numbers. The FDA (or other regulatory authority) may also request access to all study records, including source documentation, for inspection.

NO-NTM

As applicable, in accordance with the Health Insurance Portability and Accountability Act (HIPAA) and associated privacy regulations, a subject authorization to use personally identifiable health information may be required from each subject before research activities begin. This authorization document must clearly specify which parties will have access to a subject's personal health information, for what purpose, and for how long.

15.2.6 Record Retention

The investigator will maintain all study records according to GCP guidelines for a minimum of 6 years per MUSC policy.

15.3 Data Quality Assurance

The investigator will prepare and maintain adequate and accurate case histories designed to record all observations and other data pertinent to the study for each study participant. Study data for each enrolled subject will be entered into a CRF by site personnel using a secure, electronic data capture (EDC) application (REDCap).²⁰ Any changes to study data will be made to the CRF and documented in an audit trail, which will be maintained within the study database.

15.4 Data Capture

It is the investigator's responsibility to ensure the accuracy, completeness, clarity, and timeliness of the data reported in the subject's CRF. Source documentation supporting the CRF data should indicate the subject's participation in the study and should document the dates and details of study procedures, adverse events, other observations, and subject status.

The investigator will retain the CRF data and corresponding audit trails that show all updates to data, with user identification, date, and time.

15.5 Publications and Clinical Study Report

15.5.1 Publication of Study Results

Any and all scientific, commercial, and technical information in this protocol or elsewhere should be considered the confidential and proprietary property of the investigator. The investigator will be responsible for publication and/or disclosure of study results.

15.5.2 Study Report

A clinical study report will be written by the investigator and submitted to the FDA per IND requirements.

